#### **9.1.3 Serious Adverse Events (SAEs)**

An SAE is any untoward medical occurrence at any dose that:

- Results in death: This includes deaths that appear to be completely unrelated to study medication (eg, a car accident).
- Is a life-threatening event: An event that places the subject at immediate risk of death at the time of the event; it does not refer to an event that hypothetically might have caused death if it were more severe.
- Requires inpatient hospitalization or prolonged hospitalization of an existing hospitalization, unless hospitalization is for:
  - routine treatment or monitoring of the studied indication, not associated with any deterioration in condition
  - elective or pre-planned treatment for a pre-existing condition that is unrelated to the indication under study and has not worsened since signing the ICF

- treatment on an emergency outpatient basis for an event not fulfilling any of the definitions of a SAE given above and not resulting in hospital admission
- social reasons and respite care in the absence of any deterioration in the subject's general condition
- Results in permanent or prolonged (at least 28 days in duration) disability or incapacity.
- Is a congenital anomaly or birth defect in the offspring of a study subject.
- Medically important event: An event that may not be immediately life-threatening, or result in death or hospitalization, or require intervention to prevent one of the outcomes listed above, but is considered medically significant for other reasons. An opportunistic or otherwise unusual infection for the PI's practice, such as tuberculosis, will be considered medically significant.

The term severe is used to describe the intensity of a specific event (as in mild, moderate, or severe); the event itself, however, may be of minor medical significance (such as severe headache). This is not the same as serious, which is based on outcome of the event, as described above. Seriousness, not intensity, serves as a guide for defining regulatory reporting obligations.

## 9.2 Documenting and Reporting of Adverse Events (Including Serious Adverse Events)

Adverse Events will be evaluated and documented using the grading scales contained in the National Cancer Institute, Common Terminology Criteria for Adverse Events (NCI CTCAE) (Version 4.03).

### 9.2.1 Documenting and Reporting Adverse Events

All AEs reported from the time of informed consent to the end-of-study for each subject will be recorded in the subject's source documents. For subjects who do not receive study drug (ie, screen failures), AEs will only be recorded in the source documents. For subjects enrolled into the study (ie, randomized), record all AEs in the subject's AE eCRF and Clinical Trials SAE Form (if applicable). The AE CRF will indicate if the event occurred prior to the first dose of study drug, during treatment, or during the post-dosing follow-up period. Record all AEs regardless of the intensity, seriousness, or relationship to study drug.

Grade AEs (serious and non-serious) in accordance with the NCI/CTCAE scale (available at [https://evs.nci.nih.gov/ftp1/CTCAE/CTCAE\\_4.03\\_2010-06-14\\_QuickReference\\_8.5x11.pdf](https://evs.nci.nih.gov/ftp1/CTCAE/CTCAE_4.03_2010-06-14_QuickReference_8.5x11.pdf)) as presented below:

- **Mild** (Grade 1) asymptomatic or mild symptoms; clinical or diagnostic observations only; intervention not indicated
- **Moderate** (Grade 2) minimal, local or noninvasive intervention indicated; limiting age-appropriate instrumental activities of daily living

- **Severe** (Grade 3) Severe or medically significant but not immediately life-threatening; hospitalization or prolongation of hospitalization indicated; disabling; limiting self care activities of daily living
- **Life-threatening** (Grade 4) Life-threatening consequences; urgent intervention indicated
- **Death** (Grade 5) Death related to the AE.

Any recurrence of an AE with similar causality to study drug will be reported as recurrence or exacerbation of the initial event, and not as a new event. Whenever possible, report AEs as a specific diagnosis or syndrome (eg, flu syndrome) rather than as individual signs or symptoms. If no specific diagnosis or syndrome is identified, AEs should be reported as separate and individual events.

An AE includes the following:

- Progression or exacerbation of the subject's underlying disease. Clinical sequelae that result from disease progression, such as pleural effusion or small bowel obstruction, are reportable as AEs.
- Pre-existing event that increases in frequency or intensity.
- Condition detected or diagnosed during the study period, even though it may have been present, in retrospect, prior to the first dose of study drug.
- Laboratory abnormalities outside of normal limits and requiring therapeutic intervention.
- An overdose of the study drug without any signs or symptoms will be considered an AE. A calculated dose that exceeds its correct dose by 10% or more and is administered to the subject will be considered an overdose and documented as an AE.

The following events **will not** be identified as AEs in this study:

- Medical or surgical procedures (eg, surgery, endoscopy, tooth extraction, etc); however, the condition (the "triggering event") that leads to the procedure may be an AE.
- Pre-existing conditions present or detected prior to the first dose of study drug that do not worsen.

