## **9. SAFETY MONITORING AND REPORTING**

### **9.1 Definitions**

#### **9.1.1 Pretreatment Events**

A pretreatment event is any event that meets the criteria for an AE/SAE and occurs after the subject signs the ICF but before receiving the first administration of study drug.

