### 9.2.2 Assigning Attribution of Adverse Events

The Investigator must attempt to determine the cause of each event. Every effort will be made by the Investigator to assess the relationship of each AE to study drug. To ensure consistency of AE/SAE causality assessments, Investigator(s) should apply the following guideline:

**Related:** There is an association between the event and the administration of study drug, a plausible mechanism for the event to be related to the study drug and causes other than the study drug have been ruled out, and/or the event re-appeared on re-exposure to the study drug.

**Possibly Related:** There is an association between the event and the administration of the study drug and there is a plausible mechanism for the event to be related to study drug, but there may

also be alternative etiology, such as characteristics of the subject's clinical status or underlying disease.

**Unlikely Related:** The event is unlikely to be related to the study drug and likely to be related to factors other than study drug.

**Not Related:** The event is related to an etiology other than the study drug (the alternative etiology must be documented in the study subject's medical record).

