### 9.2.4 Classifying Adverse Event Outcome

For every AE/SAE, the possible outcomes of the event and the definition of the outcome are shown below in Table 16. One outcome must be entered into the appropriate field on the AE and (if appropriate) SAE form for each event as discussed in the eCRF instructions.

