10.1 Treatment Emergent Adverse Events

Adverse events will be coded using MedDRA 20.1 (September 01, 2017) and graded by CTCAE version 5 (November 27, 2017). All safety analyses and listings will be reported using the safety population. An AE will be considered a Treatment-emergent AE (TEAE) if it first occurs or begins previous to and worsens on or after the first dose date and before the last dose date + 30 days. All TEAEs will be classified as being during the on-treatment period or during the follow-up period as follows:

- Events that occurred between first dose and 7 days after last dose are classified as on-treatment;
- Events occurring between 8-30 days after last dose are classified as follow-up.

Adverse Events will be summarized for the safety population by both on-treatment period and follow-up period separately by dose group.

The following events will not be identified as AEs in this study:

- Medical or surgical procedures (e.g., surgery, endoscopy, tooth extraction, etc.). The condition (the “triggering event”) that leads to the procedure are adverse events and will be reported as such.
- Pre-existing conditions present or detected prior to the first dose of study drug that do not worsen during the study.

Summaries of Adverse Events will include the following:

- AEs that occur during the screening period will be listed in the Medical History for each subject.
- An overall summary of all TEAEs. The number of events and the number and percentage of subjects reporting at least one TEAE will be reported
- The number and percentage of subjects reporting each TEAE, categorized by MedDRA system organ class and preferred term. Note that frequencies will be by subject not event.
- The number and percentage of subjects reporting each TEAE, categorized by MedDRA system organ class, preferred term and maximum CTCAE grade
- TEAEs experienced by $\geq 5\%$ of Subjects will be summarized by preferred term
- TEAE experienced by $\geq 5\%$ of Subjects categorized by MedDRA system organ class, preferred term and maximum CTCAE grade
- Treatment Related Adverse Events categorized by MedDRA system organ class and preferred term
- The number and percentage of TEAEs with outcome of death
- Serious TEAEs categorized by MedDRA system organ class and preferred term

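### Merging AE recurrences of similar causality into the first event lowers the TEAE event count and can misplace or drop some returns

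*Protocol*

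**What the plan says.** Protocol 9.2.1 collects AEs from informed consent to the end of study and sets a rule for repeats: a recurrence whose causality to study drug is judged similar "will be reported as recurrence or exacerbation of the initial event, and not as a new event". The rule is conditional on causality. *Similar* is not defined. The same section has the AE CRF show whether an event fell before the first dose, during treatment or in follow-up.

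SAP 10.1 calls an AE treatment-emergent "if it first occurs or begins previous to and worsens on or after the first dose date and before the last dose date + 30 days". It does not define *worsens* and does not mention an event that resolves and comes back. TEAEs are then split into an on-treatment period (to 7 days after the last dose) and a follow-up period (days 8 to 30), summarised separately. For the overall summary, "The number of events and the number and percentage of subjects reporting at least one TEAE will be reported"; the SOC and preferred-term table counts subjects. AEs in the screening period go under Medical History. All AEs on the eCRF, treatment-emergent or not, are listed.

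**The concern.** AE frequency is a secondary endpoint (Protocol 2.2.2), and the TEAE tables are meant to be all-causality: SAP 10.1 has separate tables for treatment-related events. A recording rule that depends on attribution works upstream of those tables. Whether a second episode has its own record, and so its own start date, is settled by the Investigator's causality opinion before any table is made. That affects how many events are counted, which period they fall in and, in one situation, whether a subject counts as having the event at all.

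**Working it through.** The documents state no AE rate or event count, so there is no figure to reproduce. The check is to follow each kind of recurrence through the two sections.

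| First episode | Return | Merged under 9.2.1? | Result in SAP 10.1 |
|---|---|---|---|
| On drug | On drug, similar causality | Yes | One event fewer in the overall count; by-subject SOC/PT table unchanged |
| On drug | 8–30 days after last dose, similar causality | Yes | One event fewer; a single record dated by its first onset is on-treatment, so the return can be absent from the follow-up table |
| Screening, resolved | On drug, judged related or possibly related | No | New event with on-drug onset; can be a TEAE |
| Screening, resolved | On drug, no clear worsening, judged unrelated | Yes | Onset precedes first dose; a TEAE only if it *worsens*, so it can be absent even by subject |

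The third row follows from Protocol 9.1.1. A pretreatment event "occurs after the subject signs the ICF but before receiving the first administration of study drug", so it cannot have been caused by the drug. A return judged related or possibly related therefore differs in causality, and the merging rule does not reach it. A return judged unlikely related is a grey case, because *similar* is undefined.

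In the first two rows the rule applies to drug-related events as well: two on-drug episodes both judged possibly related are one event.

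The two illustrations below use assumed rates that are not in the documents.

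*Event count.* Let k be the mean number of episodes per affected subject and term, and q the share of repeat episodes judged of similar causality. The events counted per affected subject are 1 + (k − 1)(1 − q), and the understatement is 1 − [1 + (k − 1)(1 − q)]/k.
- k = 1.2, q = 0.5: counted 1.1, understatement 1 − 1.1/1.2 = 8.3%.
- k = 1.5, q = 0.8: counted 1.1, understatement 1 − 1.1/1.5 = 26.7%.
- k = 2.0, q = 1.0: counted 1.0, understatement 50%.

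By-subject incidence for on-drug repeats changes by 0% in every case.

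*Subjects missed through the fourth row.* Let n be the planned arm size (45 per active arm, 15 on placebo; Protocol 11.2), s the share with an AE that resolves in screening, r the share of those returning on drug without clear worsening as their only on-drug occurrence, and u the share of returns judged of similar causality. Subjects missed = n × s × r × u.
- Low: s = 5%, r = 20%, u = 25% gives 0.25 points, or 0.1 of 45 and 0.04 of 15.
- Middle: s = 10%, r = 50%, u = 50% gives 2.5 points, or 1.1 of 45 and 0.4 of 15.
- High: s = 20%, r = 50%, u = 100% gives 10 points, or 4.5 of 45 and 1.5 of 15.
- With u = 0, where every return is judged drug-related, none is missed.

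The range is too wide to serve as an estimate.

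**The case against.** The best defence is that little of clinical weight is lost. Returns of screening AEs attributed to the drug are new events. The main incidence table counts subjects, so repeats on drug do not move it. Every AE on the eCRF is listed, and Protocol 11.6.1 plans no testing of AEs. *Worsens* is not tied to grade: Protocol 9.2.1 treats a pre-existing event that becomes more frequent or more intense as an AE, so an event that had gone and is back could be read as worse. The eCRF instructions, which are not in the documents, may give recurrences their own dates, and the AE CRF carries a period flag. These points limit the effect, and they are why the follow-up and screening effects are stated as possible rather than certain. They do not restore the event count, and they leave the screening case without a rule.

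Three stronger readings are tempting and are not supported.
- A reader might infer that any screening AE returning on drug at the same grade is dropped. The causality condition rules that out, and neither document mentions same grade.
- A reader might infer that pruritus is undercounted more on active drug, which would shrink the difference from placebo. That requires returns caused by the drug to be judged similar in causality to a pre-drug episode, at recurrence rates the documents do not give. Possibly Related in Protocol 9.2.2 already allows for underlying disease as an alternative cause. Protocol 10.3 requires reported itch to be captured as an AE, and the VAS and 5-D scales are analysed separately.
- A reader might see contradictions with Protocol 9.2.4 ("One outcome must be entered into the appropriate field on the AE") and with 9.2.2, where support for relatedness includes that "the event re-appeared on re-exposure to the study drug". A merged record can carry its latest outcome, and 9.2.2 sets causality criteria, not record structure. The fit is awkward, but the sections do not conflict.

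**Conclusion.** The point holds in three limited parts. Merging repeats of similar causality lowers the number of events in the overall TEAE summary; this follows directly from the text. A return in days 8 to 30 after the last dose can be missing from the follow-up table when the first episode was on treatment; this assumes that a merged record keeps one start date. An AE that resolves in screening, returns on drug without clear worsening and is judged unrelated can be left out of all-causality TEAE tables; this assumes that *worsens* does not cover a simple return. The documents do not allow the size of any of these to be determined, and the percentages above only illustrate assumed rates. The primary efficacy analysis is not affected. The change is worth making because inclusion in all-causality tables should not depend on attribution.

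**What to change.** In Protocol 9.2.1, replace the recurrence sentence: a recurrence after documented resolution is entered as a new AE record with its own start date, grade, causality, action taken and outcome, flagged as a recurrence, whatever its causality. A change in an ongoing event updates the same record.

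In SAP 10.1, add that any such record starting on or after the first dose and within the 30-day window is treatment-emergent, and is assigned to the on-treatment or follow-up period by its own start date. *Worsens* would then apply only to events still ongoing at first dose, and a one-line definition would complete the rule.

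The cost is wording in the protocol, SAP and eCRF instructions, a few more AE records and slightly higher event counts. The recurrence flag still lets episodes be collapsed where a by-event summary of distinct conditions is wanted.

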### 9.2.2 Assigning Attribution of Adverse Events

The Investigator must attempt to determine the cause of each event. Every effort will be made by the Investigator to assess the relationship of each AE to study drug. To ensure consistency of AE/SAE causality assessments, Investigator(s) should apply the following guideline:

**Related:** There is an association between the event and the administration of study drug, a plausible mechanism for the event to be related to the study drug and causes other than the study drug have been ruled out, and/or the event re-appeared on re-exposure to the study drug.

**Possibly Related:** There is an association between the event and the administration of the study drug and there is a plausible mechanism for the event to be related to study drug, but there may

also be alternative etiology, such as characteristics of the subject's clinical status or underlying disease.

**Unlikely Related:** The event is unlikely to be related to the study drug and likely to be related to factors other than study drug.

**Not Related:** The event is related to an etiology other than the study drug (the alternative etiology must be documented in the study subject's medical record).

### 9.2.3 Classifying Action Taken with Study Drug

In the case of an AE, the actions that can be taken with study drug are defined below in Table 15.

**Table 15: Options for Action Taken with Study Drug**

Classification	Definition
Dose Not Changed	Study drug dose not changed in response to the AE
Dose Reduced	Study drug dose reduced in response to an AE
Drug Interrupted	Study drug administration interrupted in response to an AE
Drug Withdrawn	Study drug administration permanently discontinued in response to an AE
Not Applicable	Action taken regarding study drug administration does not apply. "Not applicable" should be used in circumstances when no opportunity to decide whether to continue, interrupt or withdraw treatment was possible such as when the investigational treatment had been completed before the adverse event began.

### 9.2.4 Classifying Adverse Event Outcome

For every AE/SAE, the possible outcomes of the event and the definition of the outcome are shown below in Table 16. One outcome must be entered into the appropriate field on the AE and (if appropriate) SAE form for each event as discussed in the eCRF instructions.

**Table 16: Classification and Definition of AE Outcomes**

Classification	Definition
Recovered / Resolved	Resolution of an AE with no residual signs or symptoms
Recovered / Resolved with sequelae	Resolution of an AE with residual signs or symptoms
Is Recovering / Is Resolving	Incomplete improvement to date but AE continues to improve/resolve and complete resolution is expected over time
Not Recovered / Not Resolved	Either incomplete improvement or no improvement of an AE, such that it remains ongoing
Fatal	Outcome of an AE is death. "Fatal" should be used when death is at least possibly related to the adverse event.
Unknown	Outcome of an AE is not known (eg, a subject lost to follow up)

### 9.2.5 Documenting and Reporting Serious Pretreatment Events and Serious Adverse Events

All SAEs that occur after obtaining informed consent through the EOS visit, regardless of causality, must be reported by the Investigator to [REDACTED] and Enanta Pharmaceuticals, Inc. In addition, all SAEs, including those that result in death, that occur after the EOS visit and that are considered related to study drug(s) must be reported to [REDACTED] and Enanta within 24 hours of learning of its occurrence. Additional details are provided in the Safety Management Plan.

The electronic SAE Form should be sent to the Study SAE e-mail address to be distributed to all recipients:

- [REDACTED]
- [REDACTED]

SAEs will be recorded on the Clinical Trials SAE Form using a recognized medical term or diagnosis that accurately reflects the event. SAEs will be assessed by the Investigator for severity, relationship to the investigational study drug(s) and possible etiologies. On the Clinical Trials SAE Form, relationship to study drug(s) will be assessed only as related or not related. For the purposes of study analysis, if the event has not resolved at the end of the study reporting period, it will be documented as ongoing. For purposes of regulatory safety monitoring, the Investigator is required to follow the event to resolution and report the outcome of the event to [REDACTED] using the SAE Form.

**The Investigator is responsible for notifying the Sponsor within 24 hours of identifying an SAE, regardless of the presumed relationship to the investigational study drug. The SAE Form should be completed for new/initial events as well as to report follow-up information on previously reported events. The Investigator is asked to report follow-up information as it becomes available.**

Enanta Pharmaceuticals, Inc. or its designees, as study sponsor, is responsible for reporting suspected, unexpected, serious adverse reactions (SUSARs) involving the study drug(s) to all regulatory authorities, and participating PIs, in accordance with FDA, ICH Guidelines, and/or local regional or country regulatory requirements, as applicable.

### **9.2.6 Documenting and Reporting of Pregnancy**

While females of childbearing potential are allowed in the study, they must agree to use two effective methods of contraception from Screening until 90 days after the last dose of study drug. However, as a precaution, subjects will be counseled to inform the Investigator of any pregnancy that occurs during study treatment and for 90 days after the last dose of study drug/s.

If a female subject or the female partner of a male subject becomes pregnant while participating in the study, study treatment must be permanently discontinued immediately. The Investigator must notify the Sponsor's Medical Monitor and [REDACTED] within one business day of the sites' knowledge of the subject's (or partner's) pregnancy, by utilizing the study-specified pregnancy report form. If confirmed to be on active drug, the subject or partner will be followed until end of pregnancy and the infant will be followed for one year after the birth, provided informed consent is obtained. A separate ICF will be provided to explain these follow-up activities. Pregnancy itself does not constitute an AE.

